**For this subject:**

	All boxes above are checked => subject satisfies all study inclusion criteria => proceed with exclusion criteria evaluation.
	One or more boxes above is not checked => subject does not satisfy all study inclusion criteria => end evaluation.

**EXCLUSION CRITERIA**

Mark each box below that applies:

	Presenting primary pain is located outside or in addition to the region of the neck (right side/left side/back) or the shoulder (right and/or left side)
	Etiology of neck/shoulder pain cannot be definitively diagnosed; or has been diagnosed as being in whole or in part other than that of osteoarthritis, chronic muscle spasms or cervical and thoracic spine sprain strain; or other potentially contributing etiologies cannot be satisfactorily ruled out
	Neck/shoulder pain is acute: symptoms prevailed for fewer than each of the prior 30 days
	Current active chronic pain disease: such as chronic fatigue syndrome and fibromyalgia
	Use of analgesics or muscle relaxants within 7 days prior to study procedure administration
	Use of systemic corticosteroid therapy (inhaled and topical corticosteroids permitted), narcotics or Botulinum toxin (Botox®) injection in the neck/shoulder region within 30 days prior to study procedure administration
	Active cancer or treatment for cancer within the last 6 months
	Unstable cardiac disease, such as recent cardiac arrhythmia, congestive heart failure or myocardial infarction
	Prior surgery to the neck/shoulder region
	Known herniated disc injury
	Active infection, wound or other external trauma to the areas to be treated with the laser
	Medical, physical or other contraindications for or sensitivity to light therapy
	Serious known mental health illness such as dementia or schizophrenia; psychiatric hospitalization in the past two years
	Pregnant or breast feeding
	Participation in a research study within the past 30 days

**For this subject:**

	No boxes checked => subject satisfies none of the exclusion criteria => proceed with study.
	One or more boxes is checked => subject satisfies one or more of the study exclusion criteria => end evaluation.

**QUALIFICATION FOR STUDY PARTICIPATION DETERMINATION**

	Subject has passed the inclusion/exclusion evaluation => subject qualifies for participation in this clinical study => proceed with the study.
	Subject has not passed either the inclusion or exclusion evaluation => subject does not qualify for participation in this clinical study => end the study.

**ERCHONIA® EVRL NECK & SHOULDER PAIN CLINICAL STUDY****PRE-PROCEDURE EVALUATIONS**Subject ID:  Investigator initials:  Date: **BASELINE VARIABLES****NECK AND SHOULDER PAIN VARIABLES****LOCATION OF PAIN:** Check all that apply.

	Right side of neck
	Left side of neck
	Back (center) or neck
	Right side of shoulder
	Left side of shoulder

**DURATION OF PAIN:** months/years since onset of first episode of neck/shoulder pain years  months**CONCOMITANT MEDICATION AND THERAPY USE**

(i) Over-the-counter and prescription medications currently used to relieve neck/shoulder pain

Medication Name	Dosage	Duration of Use	Frequency of Use

(ii) Non-drug treatments/therapies (conventional, alternative and experimental) currently used to relieve neck/shoulder pain

Treatment/Therapy	Duration of Use	Frequency of Use

(iii) Over-the-counter and prescription medications currently used, and therapies currently engaged in for any non-pain relief indication

Medication/Therapy	Indication	Dosage	Duration & Frequency of Use

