#### **CONCOMITANT MEDICATION AND THERAPY USE**

- (i) Over-the-counter and prescription medications currently used to relieve neck/shoulder pain, including duration, dosage and frequency of use
- (ii) Non-drug treatments/therapies (conventional, alternative and experimental) currently used to relieve neck/shoulder pain, including duration and frequency or use/application
- (iii) Over-the-counter and prescription medications currently used, and therapies currently engaged in for any non-pain relief indication, including duration, dosage and frequency of use

**SUBJECT DEMOGRAPHICS:** Age, gender and ethnicity

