- Physical Examination: Pain that worsens with movement (active and/or passive ROM); reduced ROM; muscle weakness; stiffness; tenderness upon palpation; possible swelling.

3. Pain is chronic: symptoms have persisted for longer than the past 30 days
4. Subject's self-reported Degree of Pain rating on the 0-100 VAS pain scale is 50 or greater
5. Subject is willing and able to refrain from consuming any over-the-counter and/or prescription medication(s) and/or herbal supplements intended for the relief of pain and/or inflammation, including muscle relaxants throughout the course of study participation,
6. Subject is willing and able to refrain from engaging in any non-study procedure therapies for the management of his or her neck/shoulder pain throughout the course of study participation, including conventional therapies such as physical therapy, occupational therapy and hot or cold packs, as well as alternative therapies such as chiropractic care and acupuncture
7. 18 years of age or older
8. Male or female
9. Primary language is English

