 Neck/shoulder pain is chronic: symptoms have persisted for longer than the past 30 days

	
Degree of Pain Self-Rating on the 0-100 Visual Analog Scale (VAS) is 50 or greater
 
Please mark with an 'X' a single spot along the 0 to 100 line below that best shows how much pain you feel right now in your neck and/or shoulder, where '0' means 'no pain' and '100' means 'worst pain imaginable'. MARK ONLY ONE SPOT. DO NOT THINK OF OR WRITE IN A NUMBER.
 
  
 
VAS Rating: _____

	Subject is willing and able to refrain from consuming any over-the-counter and/or prescription medication(s) and/or herbal supplements intended for the relief of pain and/or inflammation, including muscle relaxants throughout the course of study participation
	Subject is willing and able to refrain from engaging in any non-study procedure therapies for the management of his or her neck/shoulder pain throughout the course of study participation, including conventional therapies such as physical therapy, occupational therapy and hot or cold packs, as well as alternative therapies such as chiropractic care and acupuncture

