**COMMENTS**

## ERCHONIA® EVRL NECK & SHOULDER PAIN CLINICAL STUDY

### POST-PROCEDURE ACTIVITIES: 24 HOURS POST-PROCEDURE EVALUATION RECORDED BY THE SUBJECT AT HOME

Subject ID: \_\_\_\_\_ Investigator initials: \_\_\_\_\_ Date: \_\_\_\_\_

**This form is to be completed at 24 hours after you received the treatment with the Erchonia® EVRL Laser at the test site.**

Time of completion of this form: \_\_\_\_\_ a.m./p.m.

I have not taken any medication or done any other treatments or therapies to help with my neck and/or shoulder pain in the past 24 hours.

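### The home-form medication statement and the baseline drug list are narrower than the any-site ban on pain and anti-inflammatory drugs, so some use that breaks the ban counts as compliant

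*Combined protocol and SAP*

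**What the plan says.** **The ban.** Inclusion Criteria, item 5 requires that the "Subject is willing and able to refrain from consuming any over-the-counter and/or prescription medication(s) and/or herbal supplements intended for the relief of pain"; the item goes on to inflammation and muscle relaxants. The qualification form in Appendix C repeats it: "herbal supplements intended for the relief of pain and/or inflammation, including muscle relaxants throughout the course of study participation". Neither text limits the ban to a body site.

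**Before the procedure.** The baseline list (Concomitant Medication and Therapy Use, and the Pre-Procedure Evaluations form in Appendix C) has two medication items. Item (i) takes "Over-the-counter and prescription medications currently used to relieve neck/shoulder pain". Item (iii) takes "Over-the-counter and prescription medications currently used, and therapies currently engaged in for any non-pain relief indication". Separately, the exclusion page of Appendix C has tick boxes for "Use of analgesics or muscle relaxants within 7 days prior to study procedure administration" and for "Use of systemic corticosteroid therapy (inhaled and topical corticosteroids permitted), narcotics or Botulinum toxin (Botox®) injection in the neck/shoulder region within 30 days". A ticked box ends the evaluation.

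**After the procedure.** The 24-hour and 48-hour home forms carry one statement, covering the past 24 hours: "I have not taken any medication or done any other treatments or therapies to help with my neck and/or shoulder pain". No field is shown for the drug, the reason or the time.

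**Use of the data.** Secondary Evaluations plans a description of mean VAS at baseline, endpoint, 24 hours and 48 hours, within the dual-diode group and against the red-diode group. Primary Efficacy Outcome Statistical Evaluation restricts the per protocol set to subjects who completed according to the full protocol, and requires the ITT and per protocol analyses to agree.

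**The concern.** Item 5 itself records only willingness to abstain. Whether a subject did abstain can be learned only from the home forms, and these ask a narrower question than the ban. The case is foreseeable: the Symptoms section lists headache among the additional symptoms of the condition, and the first exclusion criterion concerns only the presenting primary pain, so subjects with lesser pain elsewhere can enrol.

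A systemic analgesic or anti-inflammatory drug can lower a neck/shoulder rating whatever it was taken for. At stake are the reading of the 24-hour and 48-hour VAS and satisfaction data as laser effect, and a per protocol set that can contain subjects who did not follow the protocol.

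**Working it through.** There is no plan figure to reproduce. The check sets the texts side by side and then gives the scale.

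**Step 1: post-procedure use.** Ban: any drug or supplement for pain or inflammation, plus muscle relaxants, at any site. Home form: medication and therapies to help the neck/shoulder pain. The part of the ban outside the statement is a pain or anti-inflammatory drug, or a muscle relaxant, taken in the 48 hours for another complaint. The statement can be truthfully affirmed after such use, and there is no field to report it.

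**Step 2: baseline list.** Item (i) covers neck/shoulder pain and item (iii) covers non-pain indications. A drug for pain at another site belongs to neither. An anti-inflammatory taken for a non-pain reason does belong in item (iii). Both items ask about current use and have no date of last use.

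**Step 3: exclusion boxes.** The analgesic and muscle-relaxant box (7 days) and the corticosteroid and narcotic entries (30 days) have no stated site limit, so a recognised user is excluded. Two uncertainties remain.
- Treatment Options lists NSAIDs such as ibuprofen and naproxen apart from analgesics such as acetaminophen and opioids, and the diagnostic criteria for osteoarthritis call Advil, Motrin and aspirin anti-inflammatory. A site could therefore leave the box empty for an NSAID taken for knee pain. Supplements are not named.
- The box is yes/no, with no drug or date to verify.

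**Step 4: what can be affected.** Endpoint evaluation occurs within 3 minutes of the procedure, so drugs taken afterwards cannot change the primary rating. They can change the 24/48-hour ratings, and they determine who belongs in the per protocol set.

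**Step 5: scale.** Inputs: n = 43 (Sample Size); reference responder rate 28/43 = 65.1% (reprinted reference publication). The number of users k and the VAS effect d are assumptions, because the documents give neither.
- One subject: 1/43 = 2.3 percentage points.
- Per protocol rate if k undetected users were removed from 28/43: (28 − k)/(43 − k) if all were responders, 28/(43 − k) if none were.
  - k = 1: 27/42 = 64.3% or 28/42 = 66.7%
  - k = 3: 25/40 = 62.5% or 28/40 = 70.0%
  - k = 6: 22/37 = 59.5% or 28/37 = 75.7%
- Shift in mean VAS at 24 or 48 hours: (k/43) × d. With k = 2 and d = 10 mm, 2/43 × 10 = 0.5 mm; with k = 9 and d = 20 mm, 9/43 × 20 = 4.2 mm.

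**The case against.** The strongest reply is that the forms do ask about off-site drugs: the exclusion boxes carry no site limit and a tick ends the evaluation. This stands. A reader might infer that such use is recorded nowhere, but before the procedure that holds only for what the boxes do not clearly name, namely NSAIDs and supplements.

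A second reply concerns the primary endpoint. A reader might reason that three subjects carried over the 30% line would add 3/43 = 7.0 points, more than the 5-point margin. The documents do not support this. Post-procedure use comes too late. A drug taken earlier and missed by the boxes would also lower the same-day baseline, and would create a responder only if its effect grew across a 13-minute procedure. Nothing shows that.

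Third, Table 3 of the reprinted publication shows 11.1% over-the-counter and 14.3% prescription use in the active arm at 24 hours. This shows that drugs were taken although subjects had been asked to refrain. It is rescue use, however, and gives no rate for other sites.

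Fourth, the VAS course is secondary and descriptive, and the exclusion of other primary pain and of chronic pain disease narrows the group at risk. Both points limit the weight of the concern. They do not remove the per protocol problem.

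Finally, the home statement could be read so that the purpose clause attaches only to treatments and therapies. It would then deny all medication, including drugs that the ban permits. That reading does not match item 5 either.

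**Conclusion.** The mismatch is real and limited. For the 48 hours after the procedure, the forms class some subjects who broke item 5 as compliant. Their 24/48-hour ratings then enter the summaries unmarked, and they stay in a per protocol set whose result must agree with ITT. Before the procedure the gap is narrower: drugs for pain elsewhere have no row in the baseline list, and the exclusion boxes leave NSAIDs and supplements uncertain.

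The primary VAS rating is not biased by post-procedure use, and the ITT result is unchanged by it. The size of the remaining effects is unknown. The per protocol rates and the 0.5 to 4.2 mm range above depend wholly on assumed k and d and show scale only. The conclusion rests on the natural reading of the home statement and on the per protocol definition covering the whole 48-hour study. The change is worth making because it is cheap and alters who counts as compliant.

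**What to change.** - **Home forms (24 and 48 hours).** Reword the statement to the scope of inclusion item 5 (any medication or supplement for pain or inflammation at any site, and muscle relaxants), plus any therapy for the neck or shoulder. Add fields for drug, reason and time taken.
- **Baseline item (i), protocol and Appendix C.** Widen it to pain or anti-inflammatory drugs and supplements at any site, with a date of last use.
- **Secondary Evaluations.** Show the 24/48-hour VAS course with and without ratings made after such use.
- **Primary Efficacy Outcome Statistical Evaluation.** State that the same record is applied when per protocol membership is decided, and how.

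The ban itself does not change. The cost is new wording on three form pages and in the matching protocol list, a few added fields, one more descriptive line and a sentence on per protocol membership. The downside is slightly longer forms, and some subjects will be recorded as non-compliant who would otherwise have passed.

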## SUBJECT DEMOGRAPHICS

## **GENDER**

Male  Female

## AGE

years

ETHNICITY

	Caucasian		Hispanic		African American
	Asian/Pacific Islander		American Indian		Other

## OUTCOME ASSESSMENTS

## **VISUAL ANALOG SCALE (VAS) DEGREE OF PAIN RATING**

Using the scale below, please mark with a cross (X) a SINGLE SPOT along the 0 to 100 line below that best shows how much **pain you feel in your neck/shoulder** right now. '0' means you feel no pain at all and '100' means you feel the worst pain imaginable. PLEASE MARK ONLY ONE SPOT. DO NOT THINK OF OR WRITE IN A NUMBER."

## LINEAR RANGE OF MOTION (ROM)

SHOULDER ROM	RIGHT SIDE MEASUREMENT (degrees)	LEFT SIDE MEASUREMENT (degrees)
Seated passive abduction		
Relaxed position of parallel to body side through full extension above head		

NECK ROM	RIGHT SIDE MEASUREMENT (degrees)	LEFT SIDE MEASUREMENT (degrees)
Measured in supine position, from forward position to face over shoulder		

## ERCHONIA® EVRL NECK & SHOULDER PAIN CLINICAL STUDY

### PROCEDURE ADMINISTRATION PHASE: PROCEDURE ADMINISTRATION RECORD

Subject ID: \_\_\_\_\_ Investigator initials: \_\_\_\_\_ Date: \_\_\_\_\_

#### PROCEDURE ADMINISTRATION RECORD

Time of Procedure Administration	Administered according to protocol?
_____ a.m. / p.m.	 Yes  No

#### COMMENTS

**ERCHONIA® EVRL NECK & SHOULDER PAIN CLINICAL STUDY****PROCEDURE ADMINISTRATION PHASE EVALUATIONS: STUDY ENDPOINT**

Subject ID:	Investigator initials:	Date:
-------------	------------------------	-------

Study endpoint evaluation has commenced within 3 minutes of completion of the procedure administration with the Erchonia® EVRL.

**OUTCOME ASSESSMENTS****VISUAL ANALOG SCALE (VAS) DEGREE OF PAIN RATING**

Using the scale below, please mark with a cross (X) a SINGLE SPOT along the 0 to 100 line below that best shows how much **pain you feel in your neck/shoulder** right now. '0' means you feel no pain at all and '100' means you feel the worst pain imaginable. PLEASE MARK ONLY ONE SPOT. DO NOT THINK OF OR WRITE IN A NUMBER."

**LINEAR RANGE OF MOTION (ROM)**

SHOULDER ROM	RIGHT SIDE MEASUREMENT (degrees)	LEFT SIDE MEASUREMENT (degrees)
Seated passive abduction		
Relaxed position of parallel to body side through full extension above head		

NECK ROM	RIGHT SIDE MEASUREMENT (degrees)	LEFT SIDE MEASUREMENT (degrees)
Measured in supine position, from forward position to face over shoulder		

**SATISFACTION WITH STUDY OUTCOME RATING:** Please ask the subject to respond to the following question by selecting the most appropriate category below.

"Overall, how satisfied or dissatisfied are you with any change in the pain in your neck and/or shoulder following the study procedure with the Erchonia® EVRL Laser?"

	Very Satisfied
	Somewhat Satisfied
	Neither Satisfied nor Dissatisfied
	Not Very Satisfied
	Not at All Satisfied

**ADVERSE EVENTS EVALUATION**

Is a potential adverse event observed by the study investigator and/or reported by the subject?

Yes => Complete investigator's adverse events form       No

**COMMENTS**

## ERCHONIA® EVRL NECK & SHOULDER PAIN CLINICAL STUDY

### POST-PROCEDURE ACTIVITIES: 24 HOURS POST-PROCEDURE EVALUATION RECORDED BY THE SUBJECT AT HOME

Subject ID: \_\_\_\_\_ Investigator initials: \_\_\_\_\_ Date: \_\_\_\_\_

**This form is to be completed at 24 hours after you received the treatment with the Erchonia® EVRL Laser at the test site.**

Time of completion of this form: \_\_\_\_\_ a.m./p.m.

I have not taken any medication or done any other treatments or therapies to help with my neck and/or shoulder pain in the past 24 hours.

#### **OUTCOME ASSESSMENTS**

##### **VISUAL ANALOG SCALE (VAS) DEGREE OF PAIN RATING**

Using the scale below, please mark with a cross (X) a SINGLE SPOT along the 0 to 100 line below that best shows how much pain you feel in your neck/shoulder right now. '0' means you feel no pain at all and '100' means you feel the worst pain imaginable. PLEASE MARK ONLY ONE SPOT. DO NOT THINK OF OR WRITE IN A NUMBER."

**SATISFACTION WITH STUDY OUTCOME RATING:** Please answer the following question by marking the most appropriate response below.

"Overall, how satisfied or dissatisfied are you with any change in the pain in your neck and/or shoulder following the study procedure with the Erchonia® EVRL Laser?"

	Very Satisfied
	Somewhat Satisfied
	Neither Satisfied nor Dissatisfied
	Not Very Satisfied
	Not at All Satisfied

#### **ADVERSE EVENTS EVALUATION**

Do you think you are experiencing an adverse event from the treatment with the Erchonia® EVRL?

Yes => Contact the investigator right away

No

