## **ADVERSE EVENTS**

At each evaluation point throughout the clinical study, and at any other time throughout the duration of the clinical trial that is necessary, any and all potential adverse events reported by a subject or observed by an investigator will be recorded on the case report form, and subsequently evaluated by a suitably qualified independent reviewer for determination of relationship to the study treatment and whether or not any corrective action needs to be taken. All potential adverse events recorded will be appropriately reported to the governing IRB, as applicable.

It is unlikely and not expected that any adverse events will result from implementation of this clinical study protocol. Prior clinical trials using low level laser light have not typically yielded any adverse events or reactions. However, potential adverse events that may feasibly occur from application of the Erchonia® EVRL include, but are not necessarily limited to: skin irritation, discoloring, rash, indentations and infection.

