## SAFETY ANALYSES

Safety analyses will be based on all enrolled subjects and will be assessed by evaluating and comparing frequency and incidence of observed and/or reported adverse events between dual-diode and red diode only procedure groups. A chi-square test with a continuity correction will be performed to compare the percentage of subjects who had adverse events between the two subject groups.

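### The 24-hour and 48-hour home forms do not ask about adverse events that have resolved or that the subject does not blame on the device, so events after the visit are likely to be under-ascertained

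*Combined protocol and SAP*

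**What the plan says.** The Adverse Events section of the protocol sets a broad rule: "any and all potential adverse events reported by a subject or observed by an investigator will be recorded on the case report form". The rule holds at every scheduled assessment, and reports outside those assessments are accepted too, "at any other time throughout the duration of the clinical trial that is necessary". Causality is left to someone other than the subject, since each recorded event is to be "evaluated by a suitably qualified independent reviewer for determination of relationship to the study treatment".

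Appendix C holds the forms that put this rule into practice.
- **On-site endpoint form**, started within 3 minutes of the end of the procedure: "Is a potential adverse event observed by the study investigator and/or reported by the subject". A positive answer leads to the investigator's adverse event form.
- **24-hour and 48-hour home forms**, completed by the subject alone: "Do you think you are experiencing an adverse event from the treatment with the Erchonia® EVRL". A positive answer carries the instruction "Contact the investigator right away". A negative answer leads to nothing. Neither form has a field for describing a symptom.
- **Investigator's adverse event record sheet**: has onset and resolution dates, and asks the investigator to explain why the event is or is not thought to result from treatment.

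The Safety Analyses section then relies on "evaluating and comparing frequency and incidence of observed and/or reported adverse events" in the dual-diode and red-diode-only groups, with a continuity-corrected chi-square test on the percentage of subjects with events.

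**The concern.** The home question applies two filters that the Adverse Events section does not call for. The first is attribution: the subject decides causality before the reviewer does. The second is timing: the question covers only the moment the form is filled in. A rash that appeared and cleared between forms, or a headache blamed on a bad night, can truthfully be answered with a no.

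These two items are the only scheduled safety follow-up for nearly all of the 48 hours after treatment, since no later visit or call is described. The study is meant to support a marketing submission for using both wavelengths together, and the reference article reports no adverse events. A zero in the new group would be read as matching that result, although part of the explanation could be the wording of the question.

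**Working it through.** The plan states no expected adverse event rate, capture rate or safety power, so there is no figure of its own to reproduce. The check is mainly a comparison of texts, followed by a labelled illustration.

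**Step 1. What a literal answer to the home item captures.**

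| Event after the visit | Subject attributes it to the device | Subject does not |
|---|---|---|
| Present when the form is completed | Yes | No |
| Resolved before the form is completed | No | No |

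One of the four kinds of event is solicited.

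**Step 2. Comparison with the rest of the plan.**
- The Adverse Events section covers potential events without regard to cause and gives the causal judgement to a reviewer. The rule applies to events reported or observed. At home nobody observes, so the form's question largely determines what is reported.
- The on-site form asks for potential events and requires no attribution.
- The investigator's sheet can hold past and unrelated events, but it is opened only once the investigator knows of one.
- The same home forms ask about medication and other therapies over the past 24 hours. Recall over an interval was therefore thought workable for those items but was not used for adverse events.

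**Step 3. Illustration for events arising after the visit.**

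Inputs:
- n = 43 (Sample Size).
- True post-visit event rate r = 10% or 5% (assumed).
- Capture fraction s = 1, 0.5 or 0.25 (assumed).

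The recorded rate is r × s, and the chance of recording no event is (1 − r × s)^43.

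| r | s | Expected recorded (43 × r × s) | Chance of none |
|---|---|---|---|
| 10% | 1 | 4.3 | 0.90^43 = 0.011 |
| 10% | 0.5 | 2.15 | 0.95^43 = 0.110 |
| 10% | 0.25 | 1.08 | 0.975^43 = 0.337 |
| 5% | 1 | 2.15 | 0.95^43 = 0.110 |
| 5% | 0.5 | 1.08 | 0.975^43 = 0.337 |
| 5% | 0.25 | 0.54 | 0.9875^43 = 0.582 |

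**Step 4. Effect on the planned test.** The comparator is taken as 0 of 43, because the reprinted article reports no events and 43 laser-treated subjects. With x events in the new group, the continuity-corrected statistic is 86 × (43x − 43)² / (43 × 43 × x × (86 − x)).
- x = 5: 86 × 172² / 748,845 = 3.40, p = 0.065.
- x = 6: 86 × 215² / 887,520 = 4.48, p = 0.034.

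Six recorded events are therefore needed for p < 0.05. With an assumed true rate of 20%, the binomial chance of recording at least six is 0.885 at full capture, 0.641 at three quarters, 0.257 at half and 0.019 at a quarter.

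**The case against.** The strongest reply is that the plan leaves other routes open. Reports are accepted at any necessary time, the on-site form takes events without attribution, the investigator's sheet has room for resolved and unrelated events, and subjects are given a contact. Subjects are also told how to complete the home forms. That instruction is not reproduced, and the consent pages are not available for review. All of this stands. A reader might infer that resolved or unattributed events can never reach the reviewer, or that the reviewer sees only events the subject has already blamed on the device. The documents support neither reading. What remains is that the plan relies on the subject volunteering what the form does not ask.

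The event rates and capture fractions are assumed. Both prior studies described in the reprinted article reported no adverse events, although how they asked is not stated. The arithmetic also does not apply to events already present at the endpoint visit, which the on-site form picks up. Both qualifications are accepted.

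Comparability is a further objection. If the reference study used a similarly narrow question, asking openly in the new group alone could create a difference through elicitation. This is a fair point, and it belongs among the costs of the change.

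Finally, safety is not part of the study success criteria, so the primary conclusion is unaffected. That is correct.

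**Conclusion.** The mismatch is on the face of the forms. After the visit, resolved or unattributed events are not solicited and may go unreported, contrary to the recording rule in the Adverse Events section and unlike the on-site form. The post-visit rate is likely to be under-ascertained.

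A reader might go further and treat an undercount of a given size as established. The documents do not allow that, since they contain no event rate and no capture rate. The rise in the chance of a zero count from 1% to 11% or 34% rests on an assumed 10% true rate, assumed capture of one half or one quarter, 43 subjects, and events arising after the visit only.

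The direction of any net bias in the comparison with the red-diode group is also unknown, because the reference study's method of eliciting events is not described. The point does not touch the efficacy conclusion, but it limits what a low or zero event count can show. It should be corrected before the forms are used.

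**What to change.** On both home forms, replace the adverse event item with an open question that requires no attribution. For example: *Since your laser procedure (48-hour form: since you completed your 24-hour form), have you had any new or worsened symptom or health problem, even if it has gone away? If yes, please describe it and give start and stop times.*

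The rest follows from that change:
- Keep the existing instruction to contact the investigator.
- Have site staff review returned forms and complete the investigator's adverse event record for every positive answer.
- Leave relationship to treatment to the independent reviewer.
- Add to Safety Analyses that the reference study's elicitation method is not described and may differ, so the between-group comparison of event rates is limited.

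The cost is the rewording of one item on two forms, more minor unrelated events to record and review, and a less favourable-looking count. Set against a reference study that reported none, part of any excess could reflect the way events were asked about, which is why the stated limitation is needed.
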